**NOTES:**

- A concomitant medication will be classed in every period of the study in which it was taken (e.g., prior to screening, run-in, on- treatment, post-treatment, post-study).
- See Section 11.6.1 for handling of partial dates.
- If the study treatment stop date is missing, it will be imputed as described in Section 11.5.1.2.

**11.3.2. All Cause Mortality**

For the summaries and analyses of the efficacy endpoint of all cause mortality, treatment phases will be defined as described in the table below after any imputation of partial death dates as described in Section 11.6.1:

Pre-treatment	Death Date < Treatment Start Date (i.e. subject did not start study treatment)
On-treatment	Treatment Start Date ≤ Death Date ≤ Treatment Stop Date + 7
Off-treatment	Subjects that prematurely discontinued study treatment that attended the Week 52 visit: Treatment Stop Date + 7 < Death Date ≤ date of Week 52 + 7  Subjects that prematurely discontinued study treatment that withdrew from the study prior to Week 52: Treatment Stop Date + 7 < Death Date ≤ projected Week 52 date + 7
Post-study	Subjects that completed study treatment: Death Date > Treatment Stop Date + 7  Subjects that prematurely discontinued study treatment that attended the Week 52 visit: Death Date > date of Week 52 + 7  Subjects that prematurely discontinued study treatment that withdrew from the study prior to Week 52: Death Date > projected Week 52 date + 7
Note: Study treatment completion is defined in Section 11.5.1.3. The projected Week 52 date is defined in Section 11.5.1.4.	

**11.3.3. Other Data**

**11.3.3.1. Post-treatment and Post-study Phases**

For all events and assessments the post-treatment and post-study phases will be defined as follows:

Post/Off-treatment	Event Onset Date or Assessment Date ≥ Treatment Stop Date + 2 AND Event Onset Date or Assessment Date ≤ study conclusion date  Note: the study conclusion date reflects the safety F/U contact for study treatment completers or the maximum of (the subjects last phone contact or their last clinic visit or the date the subject was lost to follow-up) for those subjects who discontinued study treatment prematurely.
Post-study	Event Onset Date or Assessment Date > study conclusion date.  Note: this post-study data will not be included in any summaries or analyses (but will be listed)

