4.5.3. Lost to follow-up

If a subject fails to attend the clinic for a required study visit, the site should attempt to contact the subject and re-schedule the missed visit as soon as possible. The site should also counsel the subject on the importance of maintaining the assigned visit schedule and ascertain whether or not the subject wishes to and/or should continue in the study based on previous non-compliance. In cases where the subject does not return for the rescheduled visit or cannot be reached to reschedule the missed visit, the site should make every effort to regain contact with the subject (3 telephone calls and if necessary a certified letter to the subject's last known mailing address) so that they can appropriately be withdrawn from the study. These contact attempts should be documented in the subject's medical record. If the subject continues to be unreachable, only then will he/she be considered to have withdrawn from the study with a primary reason of "Lost to Follow-up". For all other subjects withdrawing from the study, an alternative reason for

discontinuation should be recorded in the eCRF. Every effort should be made to collect survival status (whether the subject is still alive).

Note: If contact is lost with the subject, only the specific additional actions as clearly outlined in each subject's Informed Consent form (e.g. attempt contact with subject's listed contact and/or a primary care physician; request access to the subject's medical record) should be attempted to collect survival status.

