**7.3.2.3. Jump to Reference (J2R) - Using On and Off-treatment Data**

All exacerbations (on and off-treatment) will be analysed with a J2R missing data sensitivity analysis as for on-treatment exacerbations. Here however, the unobserved period will be defined for subjects that prematurely withdraw from the study from the date of study conclusion up to the projected Week 52 date (see Section 11.5.1.4). Thus, all exacerbations observed in the study will be included in this analysis, not just on-treatment exacerbations.

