#### 11.5.1.5. At Risk Period for Calculation of Raw Event Rate

##### 11.5.1.5.1. All Cause Mortality

For calculations of raw event rate the 'at risk period' in years (used for the denominator) will be defined as follows:

- On-treatment at risk period:
  - For subjects that completed the study up to Week 52 the on-treatment at risk period will derived as:  
(minimum (date of end of study treatment + 7, date of death, date of study conclusion) – date of start of treatment + 1)/365.25
  - For subjects that prematurely withdrew from the study prior to Week 52 and that have a survival status reported the on-treatment at risk period will derived as:  
(minimum (date of end of study treatment + 7, date of death, date last known alive) – date of start of treatment + 1)/365.25
  - For subjects that prematurely withdrew from the study prior to Week 52 and that do not have a survival status reported the on-treatment at risk period will derived as:  
(minimum (date of end of study treatment + 7, date of death, date of study conclusion) – date of start of treatment + 1)/365.25
- On and off-treatment at risk period:
  - For subjects that did not prematurely discontinue study treatment the on and off-treatment at risk period will derived as:  
(minimum (date of end of study treatment + 7, date of death, date of study conclusion) – date of start of treatment + 1)/365.25
  - For subjects that prematurely discontinued the study treatment period and completed the study up to Week 52 the on and off-treatment at risk period will derived as:  
(Date of study conclusion – date of start of treatment + 1)/365.25
  - For subjects that prematurely discontinued the study treatment period and prematurely withdrew from the study prior to Week 52 the on and off-treatment at risk period will derived as  
(minimum(Date last known alive, Date of Death, Projected date of Week 52 (as defined in Section 11.5.1.4) + 7) – date of start of treatment + 1)/365.25
  - For subjects that prematurely withdrew from the study prior to Week 52 and that do not have a survival status reported the on and off-treatment at risk period will derived as:  
(Date of study conclusion – date of start of treatment + 1)/365.25

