**Time to First On-treatment Exacerbation**

- The time to first on-treatment exacerbation will be calculated as exacerbation onset date of first on-treatment exacerbation – date of start of treatment + 1.
- Subjects will be represented from their Day 1 date to the start date of their first exacerbation or date of censoring. Subjects that have not experienced an on-treatment exacerbation are censored at the earliest of the date of their treatment stop date +1 day or the date of death.

COPD Exacerbations
Time to First Exacerbation Including Off-treatment data

 
The time to first exacerbation including off-treatment data will be calculated as exacerbation onset date of first exacerbation – date of start of treatment + 1.
 
Only exacerbations reported during the on-treatment and post-treatment study phases will be considered (see Section 11.3.3 for details of assigning study phase)
 
Subjects will be represented from their Day 1 date to the start date of their first exacerbation or date of censoring. Subjects that have not experienced an on or off-treatment exacerbation are censored at the earliest of (date of study conclusion or the date of death).
 

Time to First On-treatment Moderate/severe Exacerbation or Premature Study Treatment Discontinuation

 
The time to first on-treatment moderate/severe exacerbation will be calculated as exacerbation onset date of first on-treatment moderate/severe exacerbation – date of start of treatment + 1.
 
The time to study treatment discontinuation will be calculated as the date of premature study treatment discontinuation – date of start of treatment + 1.
 
The time to first on-treatment moderate/severe exacerbation or study treatment discontinuation is defined as the earliest of the time to first on-treatment moderate/severe exacerbation or time to premature study treatment discontinuation.
 
Subjects will be represented from their Day 1 date to the earliest of the event or censoring. Subjects who do not experience the event will be censored at the earliest of the date of their treatment stop date +1 day or the date of death.
 

Time to Each On-treatment Exacerbation

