**Time to On and Off-treatment All Cause Mortality**

- The time to on and off-treatment all cause mortality will be calculated as death date – date of start of treatment + 1.
- Subjects will be represented from their Day 1 date to the date of death (on and off-treatment, as defined in Section 11.3.2) or date of censoring. Subjects that have not experienced an on or off-treatment death are censored as follows:
  - Subjects that have completed study treatment are censored at the earliest of (date of study conclusion and date of study treatment stop + 7 days).
  - Subjects that prematurely discontinued study treatment that attended the Week 52 visit are censored at the earliest of (date of study conclusion and date of Week 52 + 7 days).
  - Subjects that prematurely discontinued study treatment that withdrew from the study prior to Week 52 and have a survival status present are censored at the earliest of (date last known alive and projected Week 52 date + 7).
  - Subjects that prematurely discontinued study treatment that withdrew from the study prior to Week 52 and do not have a survival status present or that have a post-study death reported are censored at the earliest of (date of study conclusion and projected Week 52 date + 7).

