**11.5.4. Safety**

**11.5.4.1. Exposure**

**Exposure**

**Exposure and Post-treatment Duration**

- Duration of exposure to study treatment is calculated as:
  - treatment stop date – treatment start date +1
- Duration of post-treatment time spent on study is calculated as:
  - study conclusion date – treatment stop date
- Duration of total time spent on study is calculated as:
  - study conclusion date – treatment start date + 1

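### Off-treatment analyses count the time between a subject's last contact and declared loss as event-free follow-up, and the date that ends follow-up ignores death

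*SAP*

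**What the plan says.** SAP 11.3.3.1 gives two rules for the study conclusion date. For those who finish treatment, "the study conclusion date reflects the safety F/U contact for study treatment completers", which is a real contact. For those who stop treatment early it is "the maximum of (the subjects last phone contact or their last clinic visit or the date the subject was lost to follow-up". Events with onset after that date are post-study and are listed but not analysed.

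The date then drives several off-treatment results:

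- **On- and off-treatment rate.** The offset (SAP 11.5.3.1) is total time in study, which SAP 11.5.4.1 defines as "study conclusion date – treatment start date + 1".
- **On- and off-treatment jump to reference (J2R).** The period to be imputed runs "from the date of study conclusion up to the projected Week 52 date" (SAP 7.3.2.3).
- **Time to first exacerbation including off-treatment data.** Event-free subjects are "censored at the earliest of (date of study conclusion or the date of death" (SAP 11.5.3.1).
- **Post-treatment event rates.** The at-risk period in SAP 11.5.1.5.2 ends at study conclusion.
- **Mortality, on and off treatment.** Withdrawn subjects with no survival status are censored no later than study conclusion (SAP 11.5.3.5).

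Death is a bound in the time-to-first censoring and in the on-treatment at-risk period. It is not a bound in the on- and off-treatment offset or in the post-treatment at-risk period.

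On when loss is declared, Protocol 4.5.3 requires rescheduling, three calls and, if necessary, a letter: "If the subject continues to be unreachable, only then will he/she be considered to have withdrawn from the study".

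**The concern.** SAP 5.2 says the off-treatment exacerbation data are there to assess how missing data affect the conclusions. An analysis with that purpose should not treat the missing period as observed. A declared-loss date later than the last contact does exactly that: the days count in the denominator or the censoring time, no event can be recorded in them, and after loss Protocol 4.5.3 provides only for tracing survival status. An arm that loses more subjects would then show too low an exacerbation rate.

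The omission of death raises a second problem. A fatal exacerbation is severe under SAP 11.5.3.1, so it belongs in the moderate/severe count. If its onset follows the last contact, the stated phase rule can remove it from every exacerbation and adverse event summary while the mortality analysis counts the same death.

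**Working it through.** The plan gives no figure for this effect, so the check applies the rules to example subjects and then sizes the result.

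**A. Lost subject.** Treatment stops on Day 100. The last phone contact is Week 28, which is Day 28 × 7 + 1 = 197. The Week 40 contact (Day 281) is missed and loss is declared on Day 300.

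- Study conclusion = max(197, 300) = Day 300.
- Time in study = 300 days (300/365.25 = 0.821 years). To the last contact it is 197 days (0.539 years).
- Unobserved but counted as event-free: 300 − 197 = 103 days.
- J2R window to Day 365: 365 − 300 = 65 days as written, against 365 − 197 = 168 days from the last contact. The J2R offset runs to projected Week 52 either way, so the 103 days are in the denominator with events neither observed nor imputed. At the planned reference rates of 0.91 and 0.94 per year (Protocol 8.2.1), that omits 0.91 × 103/365.25 = 0.26 to 0.94 × 103/365.25 = 0.27 expected events.

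**B. Off-treatment death.** Treatment stops on Day 100, the last contact is Day 197, a fatal exacerbation starts on Day 220 and death is on Day 225.

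- If the call reporting the death is not a contact, study conclusion is Day 197. Since 220 > 197, the event is post-study and excluded, and the subject is censored at Day 197 as exacerbation-free. Under SAP 11.3.2 the death is off-treatment and counted (107 < 225 ≤ 372).
- If the call is a contact, made say on Day 281, study conclusion is Day 281. The event is counted, but 281 − 225 = 56 days after death enter the offset and the post-treatment at-risk period.

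**C. On-treatment death.** Last visit Day 113, onset Day 155, treatment stop and death Day 160. Onset meets the on-treatment rule (155 ≤ 161) and, read literally, the post-study rule (155 > 113). The SAP states no precedence. The literal at-risk time is min(161, 160, 113) = 113 days.

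**D. Lost while on treatment.** Last recorded exposure is Day 113 and loss is declared on Day 250. SAP 11.5.1.2 falls back to the last exposure date, so primary at-risk time is min(114, 250) = 114 days. The loss date adds nothing.

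**Size.** The documents give neither a loss rate nor a gap, so these are assumptions. Let T be mean observed years, f the share lost and g the gap in years. An arm's rate is multiplied by T/(T + f × g).

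- *Gap.* Contacts after Week 4 are 12 weeks apart (Protocol 3.1). Adding an assumed 2 to 6 weeks of attempts gives 98 to 126 days, so g = 0.268 to 0.345. Each lost subject then hides 0.80 × 0.268 = 0.21 to 0.94 × 0.345 = 0.32 expected events.
- *2% against 5% lost, T = 0.93.* The ratio factor is (0.93 + 0.05g)/(0.93 + 0.02g) = 0.9434/0.9354 = 1.009 at 98 days, and 0.9472/0.9369 = 1.011 at 126 days. A true ratio of 0.88 reads about 0.888 to 0.890 if the comparator loses more, or 0.872 to 0.870 if triple therapy loses more.
- *Wider ranges.* With 1% to 10% lost, gaps of 2 to 16 weeks and T of 0.9 to 1.0, one arm's rate is understated by 0.04% to 3.3%. With differential loss from 2% v 4% up to 3% v 8%, gaps of 6 to 16 weeks and T = 0.95, a ratio of 0.88 becomes 0.882 to 0.894 when the comparator loses more.
- *Equal loss and gap.* The factors cancel when T is also equal, and the ratio is essentially unchanged.

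**The case against.** The strongest reply is that little depends on this. The results affected are sensitivity analyses and off-treatment summaries, the shift is about 1% even with a 2.5-fold difference in loss, and it is conservative if the comparator loses more. All of that stands, although the shift favours triple therapy if that arm loses more.

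The gap is also uncertain. Early discontinuers have an IP Discontinuation Visit and a safety contact 7 days later (Protocol 4.4.3 and 4.6), so the last contact need not be 12 weeks before the missed one. The SAP does not say that the lost date is the date of declaration. If sites record the last contact instead, the term has no effect. Since it can act only by adding unassessed time, either convention supports removing it.

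The death point depends on an unstated convention, as example B shows. Both readings go wrong, in different ways.

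Three stronger readings are tempting but not supported:

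- *That the primary result, or every missing-data analysis, is distorted.* The primary offset is capped at treatment stop + 1 and at death. On-treatment J2R imputes from treatment stop and does not use study conclusion in the offset for early discontinuers. The exacerbation-or-discontinuation analysis does not use it either.
- *That fatal events vanish.* All-cause mortality has its own phases to projected Week 52 + 7, and adjudicated cause of death is summarised including off-treatment data.
- *That mortality censoring contradicts the raw-rate denominator.* Withdrawn subjects "that have a post-study death reported are censored at the earliest of (date of study conclusion and projected Week 52 date + 7" in the Cox analysis, while the denominator uses "minimum(Date last known alive, Date of Death, Projected date of Week 52 (as defined in Section 11.5.1.4) + 7". That minimum also includes the date last known alive, which may be earlier, so a conflict is not established. Extending follow-up only for those whose later death was reported would make censoring depend on a future event, which is debatable.

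**Conclusion.** The point holds for the off-treatment analyses that use the SAP 11.3.3.1 date. Time between last contact and declared loss is treated as observed and event-free. The on- and off-treatment J2R analysis skips it. Off-treatment deaths between contacts have no coherent rule.

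The size is modest: about 1% on the rate ratio under an assumed 2% v 5% loss and a 98 to 126 day gap, and essentially nothing with equal loss. The number of off-treatment fatal events at issue cannot be estimated from the documents. The primary on-treatment analysis, on-treatment J2R, treatment completers and the counting of deaths in mortality are not affected. Example C is a gap in wording, closed by a precedence rule, and not evidence that the primary analysis is biased. The change is worth making because it is cheap and these analyses exist to test the effect of dropout.

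**What to change.** In SAP 11.3.3.1, for subjects who stop treatment early:

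1. Set study conclusion to the date of death if the subject died while still in the study. Otherwise set it to the last contact at which exacerbations and serious adverse events were assessed.
2. Remove the lost-to-follow-up date from the maximum.
3. State in SAP 7.3.2.3 that on- and off-treatment J2R imputation starts from this date.
4. State that the on-treatment phase takes precedence over post-study.

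The offset, the post-treatment at-risk period and the censoring rules then follow without separate edits, and death bounds all of them.

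The cost is a set of derivation edits with no new assessments. Because 11.3.3.1 assigns phases to most events and assessments, the affected displays need rechecking. Follow-up for lost subjects becomes slightly shorter. One real downside remains: an event learned of late, with onset after the last assessed contact, would be listed only, whereas the present maximum can retain it. The number of such events should be reported beside the sensitivity analyses.

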**11.3.3.2. Pre-treatment and On-treatment where Time is Recorded**

Any events/assessments for subjects not in the ITT population will be assigned a Pre-treatment phase.

For all events and assessments where time is recorded, the pre-treatment and on-treatment phases will be defined as follows:

Pre-treatment	Event Onset Date/Time or Assessment Date/Time $\leq$ Treatment Start Date/Time
On-treatment	Treatment Start Date/Time $<$ (Event Onset or Assessment Date/Time) $\leq$ Treatment Stop Date + 1 or any assessment with a missing or partial date unless there is evidence it was not on-treatment

**11.3.3.3. Pre-treatment and On-treatment where Time is Not Recorded**

The pre-treatment and on-treatment phases will be defined as described in the table below for the following events and assessments:

- Event-based data with an onset date reported
- Unscheduled assessments that have a date reported
- Assessments for which no planned relative time is recorded in the database, the scheduled Day 1 assessment is to be performed post-dose and have a date reported

Pre-treatment	Event Onset Date or Assessment Date $<$ Treatment Start Date
On-treatment	Treatment Start Date $\leq$ Event Onset Date or Assessment Date $\leq$ Treatment Stop Date + 1 or any assessment with a missing or partial date unless there is evidence it was not on-treatment

The pre-treatment and on-treatment phases will be defined as described in the table below for the following events and assessments:

- Assessments for which no planned relative time is recorded in the database, the scheduled Day 1 assessment is to be performed pre-dose and have a date reported

Pre-treatment	Event Onset Date or Assessment Date $\leq$ Treatment Start Date
On-treatment	Treatment Start Date $<$ Event Onset Date or Assessment Date $\leq$ Treatment Stop Date + 1 or any assessment with a missing or partial date unless there is evidence it was not on-treatment

**11.4. Appendix 4: Data Display Standards and Handling Conventions**

**11.4.1. Study Treatment and Subgroup Display Descriptors**

**11.4.1.1. Study Treatment**

Treatment Group Descriptions			
RandAll NG		Data Displays for Reporting	
Code	Description	Description	Order
1	FF/UMEC/VI 100/62.5/25	FF/UMEC/VI 100/62.5/25	1
2	FF/VI 100/25	FF/VI 100/25	2
3	UMEC/VI 62.5/25	UMEC/VI 62.5/25	3

**11.4.1.2. Treatment Comparisons**

For all analyses outputs the treatment comparisons that will be displayed are as follows:

- FF/UMEC/VI 100/62.5/25 vs. FF/VI 100/25
- FF/UMEC/VI 100/62.5/25 vs. UMEC/VI 62.5/25
- UMEC/VI 62.5/25 vs FF/ VI 100/25. Note this comparison will not be displayed on any sensitivity analyses that involve imputation.

**11.4.1.3. Eosinophils Subgroup and Display Descriptors**

Baseline eosinophil subgroup will be derived using the most recent individual eosinophil value prior to the first dose of study treatment and categorized into the following groups:

- < 0.15 10^9/L
- >= 0.15 10^9/L

Eosinophils Subgroup		
Code	Table Decode	Order
1	< 0.15 10  /L	1
2	>= 0.15 10  /L	2

**11.4.2. Baseline Definitions & Derivations**

Parameter	Study Assessments Collected Prior to Dosing		Baseline Definition
	Screening	Day 1 Pre-Dose	
Efficacy and Health Outcomes			
Trough FEV1, Trough FVC	X	X	Day 1 pre-dose and pre-bronchodilator nominal time-point
Post-bronchodilator FEV1, Post-bronchodilator FVC	X	X	Day 1 pre-dose and post-bronchodilator nominal time-point
FEV1 reversibility (mL)	X	X	Day 1 FEV1 reversibility (mL)
SGRQ total and domain scores		X	Day 1
CAT score	X	X	Day 1
EQ-5D-5L		X	Day 1
BDI (TDI Baseline)		X	Day 1
Subject global ratings		X	Day 1
Mean number of occasions of rescue use, mean number of nighttime awakenings per night	X	X	Average of measurements from Day -13 to Day 1 inclusive (at least 7 days must be non-missing)
Percentage of rescue-free days, percentage of days symptoms stopped usual activities	X	X	Percentage is calculated as total number of rescue-free days (or total number of days symptoms stopped usual activities) divided by total number of days with non-missing value (from Day -13 to Day 1 inclusive (at least 7 days must be non-missing)) x100
Safety			
Blood pressure	X		Values from most recent assessment prior to first dose of study treatment which records both systolic and diastolic BP (generally Screening but could be a test repeat).
Pulse rate	X		Most recent individual value prior to first dose of study treatment

Parameter	Study Assessments Collected Prior to Dosing		Baseline Definition
	Screening	Day 1 Pre-Dose	
Laboratory tests: Excluding hematology	X		Most recent individual value prior to first dose of study treatment
Laboratory tests: Hematology (including blood eosinophils)	X	X	Most recent individual value prior to first dose of study treatment
ECG endpoints	X		Values from most recent ECG conducted prior to first dose of study treatment

